## MEASUREMENT OF EFFECT

Although the clinical benefit of the combination of pembrolizumab and metformin has not yet been established, the intent of offering this treatment is to provide a possible therapeutic benefit, and thus the patient will be carefully monitored for tumor response and symptom relief in addition to safety and tolerability. Patients with measurable disease will be assessed by standard criteria. For the purposes of this study, patients should be re-evaluated every 9 weeks. In addition to a baseline scan, confirmatory scans will also be obtained 4 weeks following initial documentation of an objective response.

### 13.1 Antitumor Effect – Solid Tumors

For the purposes of this study, patients should be re-evaluated for response every 9 weeks. In addition to a baseline scan, confirmatory scans should also be obtained 4 weeks following initial documentation of objective response.

Response and progression will be evaluated in this study using the international criteria proposed by the revised Response Evaluation Criteria in Solid Tumors (RECIST) guideline (version 1.1) [Eur J Ca 45:228-247, 2009]. However, iRECIST will also be used if pseudoprogression is suspected. Changes in the largest diameter (unidimensional measurement) of the tumor lesions and the shortest diameter in the case of malignant lymph nodes are used in the RECIST criteria.

### 13.1.1 Definitions

Evaluable for toxicity. All patients will be evaluable for toxicity from the time of their first treatment with metformin or pembrolizumab.

Evaluable for objective response. Only those patients who have measurable disease present at baseline, have received at least one cycle of therapy, and have had their disease re-evaluated will be considered evaluable for response. These patients will have their response classified according to the definitions stated below. (Note: Patients who exhibit objective disease progression prior to the end of cycle 1 will also be considered evaluable.)

Evaluable Non-Target Disease Response. Patients who have lesions present at baseline that are evaluable but do not meet the definitions of measurable disease, have received at least one cycle of therapy, and have had their disease re-evaluated will be considered evaluable for non-target disease. The response assessment is based on the presence, absence, or unequivocal progression of the lesions.

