## SUMMARY OF PROTOCOL CHANGES

For Protocol Amendment # 5 to: # 6

UCCC Protocol #: UCCI-HN-19-01

Protocol Date: 04 Mar 2024

#	Section	Change
1	4 Eligibility	Updated Inclusion and exclusion criteria to reflect current NCI eligibility requirements with respect to brain metastases. Specifically, we have added inclusion criteria “Patients with new or progressive brain metastases (active brain metastases) are eligible if the treating physician determines that immediate CNS specific treatment is not required and is unlikely to be required during the first cycle of therapy.” And we have removed exclusion criteria “Patients with known active brain metastases, given that there is a chance for increasing edema with immunotherapy and active brain metastases. See inclusion #9 for requirements for participation for patients with treated brain metastases.”
2	10.4 Randomization	Added clarification that if screening labs are to be obtained on same day as treatment randomization may be performed at the time all other eligibility criteria are informally confirmed to allow adequate time for treatment planning
3	SOE	Removed text “Baseline evaluations are to be conducted within 10 days prior to start of protocol therapy. Scans and x-rays must be done <4 weeks prior to the start of therapy. Following registration, patients should begin protocol treatment within 28 days.” From before SOE as it is duplicative with other areas of the protocol.
4	Various	Other grammatical and formatting changes throughout
5	10.2 Sample Size/Accrual Rate	Updated the overall accrual from 20 subjects to 25 subjects due to the higher than expected withdraw rate before starting or reaching steady state of metformin on arm 2. The stats and enrollment report have been updated as well to reflect this increase in accrual.
6	Various	Although Protocol Amendment v5 dated 05Feb2024 has been IRB approved, these changes to the protocol were based upon updates made to Protocol v1 dated 22Jun2020 rather than the most recently approved prior version Protocol Amendment v4 dated 16 Sept 2022. Protocol v6 is being submitted to incorporate the previously IRB approved update to increase the overall accrual from 20 subjects to 25 subjects into the protocol v4’s content.

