### 2.2 Secondary Objective

- (1) To observe and record safety and toxicity of combination, progression free survival and overall survival in recurrent and/or metastatic HNSCC patients receiving the combination of metformin and pembrolizumab.

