#### 7.4.1 Metformin

##### *Treatment:*

Patients will receive metformin ER starting on day -14 for arm 1 and Day -7 for arm 2. The starting dose will be 1000mg PO daily to be administered with evening meal. The tablet should be swallowed whole, and patients will be instructed not to crush, cut or chew medication. On day -7 (or Day 1 for arm 2), patients will increase to 2000mg daily. Metformin will be continued daily with pembrolizumab.

Metformin should continue throughout treatment and even through pembrolizumab delays unless patient is experiencing adverse effects attributed to metformin. Metformin should be taken with food at approximately the same time daily. Patients will be instructed to check their blood sugar if they have any symptoms of hypoglycemia including but not limited to chills/shakiness, cold feeling, lightheadedness, dizziness, etc. Patients will be given a diary to record each dose. They should also be warned that the shell of the ER tablet may be visible in stool and not to be alarmed.

NOTE: Temporarily discontinue metformin in patients undergoing radiologic studies in which intravascular iodinated contrast media are utilized. It is generally recommended that metformin be temporarily discontinued prior to or at the time of intravascular administration of iodinated contrast media (potential for acute alteration in renal function). Continue to withhold metformin for 48 hours after the radiologic study.

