## STATISTICAL CONSIDERATIONS

### 10.1 Study Design/Endpoints

Primary Endpoint: Overall Response by RECIST 1.1 and iRECIST

Responses will be summarized as frequencies and percentages.

Secondary Endpoints:

- Measurement of Adverse Events by CTCAE v5.0
- Progression Free Survival (PFS) at 1 year
- Overall Survival (OS) at 1 year

After cleaning and preprocessing of the collected data, descriptive statistics will be used to summarize all adverse events. Toxicities will be aggregated as the number and percentage of patients with each type of toxicity. Kaplan Meier methods will be used to estimate overall survival and progression free survival generating median survival estimates with 95% confidence intervals (95% CIs). Multivariable survival modeling (overall survival and progression free survival) will be performed using Cox proportional hazards models and to generate Hazard Ratios (HR) and 95% CIs, with adjustment for potential patient confounders such as age, sex, smoking status, etc.

Exploratory Endpoint:

- Characterization of peripheral blood immune cell phenotypes before and after metformin, pembrolizumab and combination treatment with a particular focus on Natural Killer (NK) cells and innate immunity.
- Characterization of tumor infiltrating NK cells before and after metformin, pembrolizumab and combination treatment.
- Cytokine levels before and after metformin, pembrolizumab and combination in the plasma.
- NK effector functions before and after metformin, pembrolizumab and combination.
- Stat-3 RNA levels and phosphorylation status in NK cells and tumor tissue before and after metformin, pembrolizumab and combination treatment.
- Level of NKG2D soluble ligands before and after metformin, pembrolizumab and combination in the plasma.

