### 10.4 Randomization:

Patients will be randomized into arms 1 and 2 using R (R Core Team. 2012) at time of registration (if screening labs are to be obtained on same day as treatment randomization may be performed at the time all other eligibility criteria are informally confirmed to allow adequate time for treatment planning). The UC Project Manager will work with the statistician to ensure each patient is assigned to one of the arms correctly. Randomization of patients does not affect the primary or secondary endpoints of this study as response and safety is based on the combination treatment in which both groups will receive. The patients are randomized for the exploratory endpoints in order to better understand the difference of effects of metformin versus pembrolizumab on the immune system.

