
c. Only applies to Arm 2 as Arm 1 does not have a D -21.
 
d. Full physical exam at screening, directed on other visits
 
e. Child-bearing females only. Test within 72 hours of first treatment (See 7.6.1)
 
f. See table 1 in section 7.5.7
 
g. Archival acceptable at screening; Cycle 2 repeat biopsy if clinically feasible. Biopsy may be of a target or non-target lesion but if there is only one target lesion that is being followed, this lesion should be avoided for biopsy unless discussed with PI.
 
h. 60mls in EDTA tubes and 5mls in red top serum tube at Day -14 (Arm 1) or Day -21 (Arm 2); and also collect Day 1 (Arm 1) or Day -7 (Arm 2); and also collect Cycle 2 Day 1 (week 4). The Day -14 & Day -21 respective samples must be collected before any study treatment is given on those days – if this pre-treatment sample is missed then no other blood correlatives should be collected for those subjects. This first pre-treatment correlative blood sample may be obtained at another time-point after randomization but prior to first lead in treatment with the PI's approval.
 
i. Should be completed at 30 days post-treatment OR before new anti-cancer therapy whichever occurs first.
 
j. Every 3 months/12 weeks - can be completed by telephone
 
k. ECOG PS and screening laboratory tests to be completed within 10 days of first tx (may be performed on day 1 prior to tx)
 
l. Scans to be performed every 12 weeks +/- 5 days starting with C3D1
 
m. Adverse events should be collected for 90 days following the last dose of study treatment
 
n. Subjects will be provided with a medication diary at screening but will not complete entries until dispensed Metformin. The medication diary will be returned to research staff and a new diary issued at the end of each course.
 
o. Subjects are randomized to either Arm 1 or Arm 2 after registration (eligibility is confirmed). These arms are independent of each other. Each arm has the same amount of time 28 days, to complete screening activities before their respective first lead in treatment visits (Day -21 or Day -14).
 
p. Pembrolizumab may be given at 200mg q3 weeks or 400mg q6 weeks and may be changed during course of treatment per investigator discretion.
 
q. Temporarily discontinuing metformin in patients undergoing radiologic studies in which intravascular iodinated contrast media are utilized is left up to investigator discretion.
										

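### The planned toxicity percentage pools single-agent lead-in with combination treatment, so it does not isolate the combination toxicity that the secondary objective names

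*Combined protocol and SAP*

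**What the plan says.** - **Target.** Section 2.2 sets the safety objective as "To observe and record safety and toxicity of combination". Section 10.4 explains why randomization is irrelevant to the primary and secondary endpoints: "response and safety is based on the combination treatment in which both groups will receive".
- **Evaluable set.** Section 13.1.1: "All patients will be evaluable for toxicity from the time of their first treatment with metformin or pembrolizumab".
- **Summary.** Section 10.1: "Toxicities will be aggregated as the number and percentage of patients with each type of toxicity". No denominator is named, and there is no split by period, arm or exposure to both drugs.
- **Lead-in.** Section 7.4.1: "Patients will receive metformin ER starting on day -14 for arm 1 and Day -7 for arm 2". The study calendar (Section 12) gives Arm 2 its first pembrolizumab at Day -21 and Arm 1 its first at Day 1.
- **Early withdrawal.** Item 5 of the Summary of Protocol Changes raises accrual from 20 to 25 because of a "higher than expected withdraw rate before starting or reaching steady state of metformin on arm 2".

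No section defines a set of patients exposed to both drugs for the toxicity tables.

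**The concern.** Sections 2.2 and 10.4 point to one quantity, and 13.1.1 with 10.1 delivers another. A patient who leaves before the second drug cannot have an event on the combination, yet is evaluable for toxicity from the first dose. A patient with, say, diarrhea on metformin alone in the Arm 1 lead-in counts as having that toxicity, although no pembrolizumab had been given.

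Section 3.3 notes that the safety of the pair is documented only at lower metformin doses than the one planned here, so readers will look to the final adverse event tables for combination toxicity. Overlapping toxicities are the hardest to read. Diarrhea is listed for pembrolizumab in 3.2.1 and as the main cause of stopping metformin in 3.2.2, and a pooled percentage cannot show how much of it arose on both drugs.

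**Working it through.** **The plan's own figures.** The plan states no toxicity rate or toxicity precision, so there is none to reproduce. The enrolment figures in 10.2 do reproduce approximately: 19/(1 - 0.20) = 23.75, rounded up to 24, against 25 planned. Conversely, 25 x 0.80 = 20, and 19 of 25 evaluable is a 24% loss.

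**Time on one agent.** Arm 1 has metformin alone from Day -14 until pembrolizumab on Day 1. Arm 2 has pembrolizumab alone from Day -21 until metformin on Day -7. That is about 14 days in each arm.

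**Inputs for the illustration.** N = 25 treated, taking all planned patients as treated. The other three are assumptions, because the documents give none of them:
- k = treated patients who never receive both drugs, 1 to 6. The upper end is 25 - 19 = 6, which treats every non-evaluable patient as dosed but never on both.
- p = risk of a given toxicity during combination treatment, 30%.
- q = risk of the same toxicity during the single-agent lead-in, 0% to 20%, with the two periods independent.

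**Formulas.**
- Combination-period events over all treated: p(25 - k)/25.
- Pooled, as 13.1.1 and 10.1 read together: [(25 - k)(1 - (1 - p)(1 - q)) + kq]/25.
- Lead-in risk at which the two effects cancel: q = kp/[(25 - k)(1 - p) + k].

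**Worked case, p = 30%, k = 3.**
- q = 0%: 22 x 0.30/25 = 26.4%.
- q = 10%: (22 x 0.37 + 0.3)/25 = 8.44/25 = 33.8%.
- q = 20%: (22 x 0.44 + 0.6)/25 = 10.28/25 = 41.1%.
- Cancelling point: 0.9/(22 x 0.7 + 3) = 0.9/18.4 = 4.9%.

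**Range over k, p = 30%.**

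| k | q = 0% | q = 10% | q = 20% | effects cancel at q |
|---|---|---|---|---|
| 1 | 28.8% | 35.9% | 43.0% | 1.7% |
| 3 | 26.4% | 33.8% | 41.1% | 4.9% |
| 6 | 22.8% | 30.5% | 38.2% | 9.3% |

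The same 30% combination risk can be reported well below or well above 30%. The direction turns on k and q, and the planned table shows neither.

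**The case against.** **An all-treated set from first dose is a conventional safety population.** This stands. Section 13.1.1 is not an error in itself. The gap is that no further summary matches the stated objective.

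**The protocol treats the lead-in as part of judging the combination.** Section 7.7.2 counts dose-limiting toxicities in the lead-in as well as in the first 28 days on both drugs, and 10.3 uses them to verify the combination's safety. This is a fair reading of the stopping rule. That rule covers the first nine patients only and does not make the final percentages a measure of toxicity on both drugs.

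**A reader might infer that the percentages are simply diluted, by 12% to 24% if 3 to 6 of 25 patients never had both drugs.** The documents do not support this, for three reasons.
- Section 10.1 names no denominator; all-treated is inferred from 13.1.1.
- The number never on both drugs is not given. The withdrawals in the amendment summary include patients who had started metformin and so had both drugs. Patients never dosed fall outside 13.1.1. The gap between 25 and 19 is non-evaluability, which 10.2 links to drop-out, and a patient on both drugs for weeks can still lack a response assessment.
- The pure reduction requires no lead-in events at all. At p = 40% the bias is already zero at q of about 7% for k = 3 (1.2/16.2) and 14% for k = 6 (2.4/17.4), and it reverses above that.

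**A combination-only table has its own bias.** This also stands. It drops patients who stopped for lead-in toxicity, and late pembrolizumab effects, which 8.2 says may appear months after a dose, would still fall in the combination period.

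**No decision depends on the figure, and the split could be made at reporting.** Also true. It limits the weight of the point, but naming the tables and denominators in advance is better than choosing them after the data are seen.

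**Conclusion.** The point holds as a mismatch between objective and analysis. Sections 2.2 and 10.4 name toxicity of the combination; 13.1.1 and 10.1 give a percentage that mixes about 14 days of single-agent treatment with combination treatment and may include patients never on both drugs.

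The net bias can go either way, and the documents do not allow it to be sized. The 26.4% to 41.1% spread around a 30% risk rests on assumed values of k, p and q, on 25 treated patients and on independent periods. It shows how far the figure could move and is not an estimate for this trial. Neither a net understatement nor a defect in the all-treated set is established.

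The weight is moderate. The endpoint is secondary, descriptive and untested, and neither the 6 of 19 response criterion nor the stopping rule uses it. The change is still worth making because it is cheap and supplies the estimate the objective asks for.

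**What to change.** In 10.1 and 13.1.1:

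1. Keep the all-treated table, covering all patients from the first dose of either drug, and state its denominator.
2. Add a combination-period table limited to patients who received at least one dose of both drugs, counting events with onset from the first day on both. State how an event that begins in lead-in and worsens later is counted; 11.6 already has each grade change recorded.
3. Show lead-in events separately for Arm 1 (metformin alone) and Arm 2 (pembrolizumab alone), each over the patients who entered that lead-in.
4. Reconcile the wording of 13.1.1 with 10.4, which assumes that both groups receive the combination.

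**Cost.** Two or three more tables and a few lines of text. Section 11.4 collects adverse events continuously from the start of study drug, so no new data should be needed provided onset and first-dose dates are recorded. The combination denominator is smaller. At 30%, a normal-approximation 95% half-width goes from 1.96 x sqrt(0.21/25) = 18.0 points to 1.96 x sqrt(0.21/22) = 19.1 points if 3 patients are removed. The combination set is also selected for tolerating the lead-in and may still contain late single-agent effects. It should be read beside the all-treated table and not replace it.

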### 13.1.2 Disease Parameters

Measurable disease. Measurable lesions are defined as those that can be accurately measured in at least one dimension (longest diameter to be recorded) as  $\geq 20$  mm ( $\geq 2$  cm) by chest x-ray or as  $\geq 10$  mm ( $\geq 1$  cm) with CT scan, MRI, or calipers by clinical exam. All tumor measurements must be recorded in millimeters (or decimal fractions of centimeters).

Note: Tumor lesions that are situated in a previously irradiated area might or might not be considered measurable. If the lesion has progressed after radiation treatment, then it may be considered evaluable.

Malignant lymph nodes. To be considered pathologically enlarged and measurable, a lymph node must be  $\geq 15$  mm ( $\geq 1.5$  cm) in short axis when assessed by CT scan (CT scan slice thickness recommended to be no greater than 5 mm [0.5 cm]). At baseline and in follow-up, only the short axis will be measured and followed.

Non-measurable disease. All other lesions (or sites of disease), including small lesions (longest diameter  $< 10$  mm [ $< 1$  cm] or pathological lymph nodes with  $\geq 10$  to  $< 15$  mm [ $\geq 1$  to  $< 1.5$  cm] short axis), are considered non-measurable disease. Bone lesions, leptomeningeal disease, ascites, pleural/pericardial effusions, lymphangitis cutis/pulmonitis, inflammatory breast disease, and abdominal masses (not followed by CT or MRI), are considered as non-measurable.

Note: Cystic lesions that meet the criteria for radiographically defined simple cysts should not be considered as malignant lesions (neither measurable nor non-measurable) since they are, by definition, simple cysts.

‘Cystic lesions’ thought to represent cystic metastases can be considered as measurable lesions, if they meet the definition of measurability described above. However, if non-

cystic lesions are present in the same patient, these are preferred for selection as target lesions.

Target lesions. All measurable lesions up to a maximum of 2 lesions per organ and 5 lesions in total, representative of all involved organs, should be identified as **target lesions** and recorded and measured at baseline. Target lesions should be selected on the basis of their size (lesions with the longest diameter), be representative of all involved organs, but in addition should be those that lend themselves to reproducible repeated measurements. It may be the case that, on occasion, the largest lesion does not lend itself to reproducible measurement in which circumstance the next largest lesion which can be measured reproducibly should be selected. A sum of the diameters (longest for non-nodal lesions, short axis for nodal lesions) for all target lesions will be calculated and reported as the baseline sum diameters. If lymph nodes are to be included in the sum, then only the short axis is added into the sum. The baseline sum diameters will be used as reference to further characterize any objective tumor regression in the measurable dimension of the disease.

Non-target lesions. All other lesions (or sites of disease) including any measurable lesions over and above the 5 target lesions should be identified as **non-target lesions** and should also be recorded at baseline. Measurements of these lesions are not required, but the presence, absence, or in rare cases unequivocal progression of each should be noted throughout follow-up.

### 13.1.3 Methods for Evaluation of Measurable Disease

All measurements should be taken and recorded in metric notation using a ruler or calipers. All baseline evaluations should be performed as closely as possible to the beginning of treatment and never more than 4 weeks before the beginning of the treatment.

The same method of assessment and the same technique should be used to characterize each identified and reported lesion at baseline and during follow-up. Imaging-based evaluation is preferred to evaluation by clinical examination unless the lesion(s) being followed cannot be imaged but are assessable by clinical exam.

Clinical lesions: Will only be considered measurable when they are superficial (*e.g.*, skin nodules and palpable lymph nodes) and  $\geq 10$  mm ( $\geq 1$  cm) diameter as assessed using calipers (*e.g.*, skin nodules). In the case of skin lesions, documentation by color photography, including a ruler to estimate the size of the lesion, is recommended.

Conventional CT and MRI: This guideline has defined measurability of lesions on CT scan based on the assumption that CT slice thickness is 5 mm (0.5 cm) or less. If CT scans have slice thickness greater than 5 mm (0.5 cm), the minimum size for a measurable lesion should be twice the slice thickness. MRI is also acceptable in certain situations (*e.g.* for body scans).

Use of MRI remains a complex issue. MRI has excellent contrast, spatial, and temporal resolution; however, there are many image acquisition variables involved in MRI, which

greatly impact image quality, lesion conspicuity, and measurement. Furthermore, the availability of MRI is variable globally. As with CT, if an MRI is performed, the technical specifications of the scanning sequences used should be optimized for the evaluation of the type and site of disease. Furthermore, as with CT, the modality used at follow-up should be the same as was used at baseline and the lesions should be measured/assessed on the same pulse sequence. It is beyond the scope of the RECIST guidelines to prescribe specific MRI pulse sequence parameters for all scanners, body parts, and diseases. Ideally, the same type of scanner should be used and the image acquisition protocol should be followed as closely as possible to prior scans. Body scans should be performed with breath-hold scanning techniques, if possible.

PET-CT: At present, the low dose or attenuation correction CT portion of a combined PET-CT is not always of optimal diagnostic CT quality for use with RECIST measurements. However, if the site can document that the CT performed as part of a PET-CT is of identical diagnostic quality to a diagnostic CT (with IV and oral contrast), then the CT portion of the PET-CT can be used for RECIST measurements and can be used interchangeably with conventional CT in accurately measuring cancer lesions over time. Note, however, that the PET portion of the CT introduces additional data which may bias an investigator if it is not routinely or serially performed.

Ultrasound: Ultrasound is not useful in assessment of lesion size and should not be used as a method of measurement. Ultrasound examinations cannot be reproduced in their entirety for independent review at a later date and, because they are operator dependent, it cannot be guaranteed that the same technique and measurements will be taken from one assessment to the next. If new lesions are identified by ultrasound in the course of the study, confirmation by CT or MRI is advised. If there is concern about radiation exposure at CT, MRI may be used instead of CT in selected instances.

Endoscopy, Laparoscopy: The utilization of these techniques for objective tumor evaluation is not advised. However, such techniques may be useful to confirm complete pathological response when biopsies are obtained or to determine relapse in trials where recurrence following complete response (CR) or surgical resection is an endpoint.

Cytology, Histology: These techniques can be used to differentiate between partial responses (PR) and complete responses (CR) in rare cases (*e.g.*, residual lesions in tumor types, such as germ cell tumors, where known residual benign tumors can remain).

The cytological confirmation of the neoplastic origin of any effusion that appears or worsens during treatment when the measurable tumor has met criteria for response or stable disease is mandatory to differentiate between response or stable disease (an effusion may be a side effect of the treatment) and progressive disease.

FDG-PET: While FDG-PET response assessments need additional study, it is sometimes reasonable to incorporate the use of FDG-PET scanning to complement CT scanning in assessment of progression (particularly possible 'new' disease). New lesions on the basis of FDG-PET imaging can be identified according to the following algorithm:

- a. Negative FDG-PET at baseline, with a positive FDG-PET at follow-up is a sign of PD based on a new lesion.
- b. No FDG-PET at baseline and a positive FDG-PET at follow-up: If the positive FDG-PET at follow-up corresponds to a new site of disease confirmed by CT, this is PD. If the positive FDG-PET at follow-up is not confirmed as a new site of disease on CT, additional follow-up CT scans are needed to determine if there is truly progression occurring at that site (if so, the date of PD will be the date of the initial abnormal FDG-PET scan). If the positive FDG-PET at follow-up corresponds to a pre-existing site of disease on CT that is not progressing on the basis of the anatomic images, this is not PD.
- c. FDG-PET may be used to upgrade a response to a CR in a manner similar to a biopsy in cases where a residual radiographic abnormality is thought to represent fibrosis or scarring. The use of FDG-PET in this circumstance should be prospectively described in the protocol and supported by disease-specific medical literature for the indication. However, it must be acknowledged that both approaches may lead to false positive CR due to limitations of FDG-PET and biopsy resolution/sensitivity.

Note: A 'positive' FDG-PET scan lesion means one which is FDG avid with an uptake greater than twice that of the surrounding tissue on the attenuation corrected image.

